### 9.3.2. Interim Analysis

A formal interim analysis will be conducted during the study. Additionally two review teams will monitor data on an ongoing basis for routine pharmacovigilance and decision making regarding the subsequent clinical development of GSK2982772 for RA.

In line with routine pharmacovigilance, an internal GSK Safety Review Team (SRT) which will include members of the GSK2982772 project team, will review blinded safety

data, including clinical laboratory parameters and adverse events, at appropriate intervals during the period of study conduct.

Once an appropriate number of subjects have completed Day 43 (Week 6) the DAS28-CRP data will be reviewed in an unblinded manner and on an ongoing basis by the Data Review Committee, consisting of the GSK Project Physician Lead (PPL), the study statistician, the study pharmacokineticist, the PRR DPU Head, EDL and SRT Leader or designees on an ongoing basis. A physician external to the GSK2982772 project team may also be involved in the data review. Additional inflammatory biomarkers, clinical and mechanistic endpoints (e.g. target engagement) may be reviewed if available. No other member of the GSK core study team will be unblinded to this data. The primary purpose of these informal reviews will be to monitor DAS28-CRP for futility. On review of DAS28-CRP data, the review group may recommend an interim analysis of key clinical and mechanistic data is first conducted prior to any decision to terminate the study for futility. A data review charter will identify the specific GSK individuals involved, outline in detail the activities of this review and how the integrity of the study will be maintained.

A formal interim analysis will be conducted during the study. The timing of this analysis will either be on the recommendation of the data review group to assess futility based on 6 weeks of treatment, or when an appropriate number have completed 12 weeks of treatment, whichever is earliest. The purpose of the Interim Analysis would be to assess whether to stop the study for futility. This interim analysis may also facilitate decision making regarding the subsequent clinical development of GSK2982772 for RA.

#### **9.4. Key Elements of Analysis Plan**

##### **9.4.1. Primary Analyses**

All safety evaluations will be based on the Safety population. Clinical interpretation will be based on the review and displays of adverse events, clinical laboratory values, vital sign measurements and 12-lead ECG monitoring.

##### **9.4.2. Secondary Analyses**

The relationship between each of the mechanistic endpoints and also with the clinical endpoints will be graphically presented and analysed using an appropriate statistical model identifying any trends. The model will determine whether the mechanistic effect significantly explains or predicts the effect on the other mechanistic or clinical endpoints (e.g., DAS28-CRP score). This may be conducted through comparing statistical models incorporating different explanatory terms (i.e. mechanistic endpoints) with the 'null' model (no mechanistic endpoints); or if deemed appropriate, multivariate statistical methods may also be applied to determine the relationship between the key endpoints. The consistency in the changes over time between the endpoints will also be assessed.

Each endpoint will be considered individually and at the treatment level, where comparisons between treatment groups would be made on any changes observed, if deemed appropriate. This could include change from baseline in DAS28-CRP, which will be statistically analysed using a MMRM analysis comparing GSK2982772 with placebo

at each time point. Additionally this could include, the proportion of subjects achieving ACR20/50/70 and DAS28-CRP response, which will be statistically analysed using a Generalised Estimating Equation (GEE) model comparing GSK2982772 with placebo at each timepoint. Similar analyses will be conducted for other secondary endpoints if deemed appropriate.

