### Objective(s)/Endpoint(s)

Objectives	Endpoints
Primary	

 
To investigate the safety and tolerability of 60 mg three times daily doses of GSK2982772 in subjects with moderate to severe Rheumatoid Arthritis.
 
	
 
Adverse events.
 
Clinical laboratory values (clinical chemistry, haematology and urinalysis).
 
Vital sign measurements (blood pressure, heart rate, respiratory rate, and body temperature).
 
12-Lead ECG monitoring.
 

Secondary	

 
To investigate the plasma concentrations of GSK2982772 following 60 mg three times daily doses of GSK2982772 in subjects with moderate to severe Rheumatoid Arthritis.
 
	
 
Pre-dose concentrations of GSK2982772 on Days 8 and 43 (Week 6).
 
Post-dose concentrations of GSK2982772 on Days 1, 8, and 43 (Week 6) at 1, 2, 4 and 6 hours.
 
Trough concentrations on Day 85 (Week 12).
 

 
To investigate the effect of 60 mg three times daily doses of GSK2982772 on inflammatory biomarkers in blood subjects with moderate to severe Rheumatoid Arthritis.
 
	
 
Change from baseline in blood inflammatory markers (e.g., may include but not limited to CRP, IL6, MMP-1, MMP-3, MMP-13, TIMP-1, MCP-1, MIF, MRP8/14 and other markers encompassed by Vectra DA).
 

Objectives	Endpoints

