### **4.4. Design Justification**

As this is the first trial of GSK2982772 in subjects with RA, the primary endpoint is the safety and tolerability of GSK2982772. In addition, this study will include assessments of target engagement and downstream PD effects of GSK2982772, to understand whether GSK2982772 is inhibiting the pathway of interest in this disease.

The 12 week duration of treatment is based on review of previous proof of mechanism and proof of concept studies in RA and is limited by the supporting 13 week toxicology studies. It is expected that an effective therapy should cause group level changes in the mechanistic parameters by the 12 week time point.

The subjects will be randomised in a 2:1 ratio to GSK2982772 60 mg three times daily (TID) and placebo respectively. The primary objective of this study is to assess safety and tolerability, and assessment of this is most valuable in a placebo controlled study.

The placebo group was also deemed necessary as autoimmune diseases naturally fluctuate in severity. However, the size of the placebo group has been kept to a minimum. All subjects will be allowed to continue standard of care therapy including non-biologic DMARDs during the study, provided that the medication and dose is stable throughout the study.

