### **7.4.2.4. Measurement of Serum CRP**

Blood samples will be collected in order to measure serum CRP concentrations. The CRP is a component of the DAS28, ACR, and Vectra DA clinical scores.

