## 9. STATISTICAL CONSIDERATIONS AND DATA ANALYSES

### 9.1. Hypotheses

The primary objective of the study is to investigate the safety and tolerability of GSK2982772 following 12 weeks of treatment. No formal statistical hypotheses will be conducted to assess this objective.

If appropriate, comparisons between the GSK2982772 and the placebo arm will be made to investigate the secondary pharmacodynamic, mechanistic and efficacy objectives.

Trends over time will be investigated for both treatment arms along with associations between each of the pharmacodynamic, mechanistic and efficacy parameters.

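### Section 9.4.2 promises to show that a mechanistic effect explains a clinical effect, but the comparison it describes shows association only, and is partly circular where CRP sits on both sides

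*Protocol*

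**What the plan says.** Protocol Section 9.4.2 (Secondary Analyses) states the aim: "The model will determine whether the mechanistic effect significantly explains or predicts the effect on the other mechanistic or clinical endpoints", with DAS28-CRP as its example. It says this may be done by "comparing statistical models incorporating different explanatory terms (i.e. mechanistic endpoints) with the 'null' model (no mechanistic endpoints", and adds an alternative: "if deemed appropriate, multivariate statistical methods may also be applied to determine the relationship between the key endpoints". It does not say whether treatment arm or baseline values enter either model. It also has no step that ties the drug's effect on a marker to its effect on the clinical score.

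Section 9.1 sets the scope of the pairings: it will look at "associations between each of the pharmacodynamic, mechanistic and efficacy parameters". The objectives table lists, as a secondary endpoint, "Change from baseline in blood inflammatory markers (e.g., may include but not limited to CRP, IL6", and continues to markers covered by Vectra DA. Section 7.6 also places Vectra DA markers among the pharmacodynamic biomarkers. Section 7.4.2.4 states: "The CRP is a component of the DAS28, ACR, and Vectra DA clinical scores". Nowhere does the protocol define a disease activity outcome without CRP or caution about the overlap.

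The synopsis says that no formal hypothesis is tested. Section 9.4.3 leaves further statistical detail to the Reporting and Analysis Plan (RAP), which is not available here.

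**The concern.** The claim is about effects: the drug moves the marker, and that movement accounts for the clinical improvement. The comparison is about association: does adding the marker improve the fit? The null hypothesis it rejects is that marker change and outcome change are unrelated. That null can be false for reasons unrelated to mechanism.

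Two such reasons lie within what the plan allows. If the marker is CRP, or the Vectra DA score, and the outcome is DAS28-CRP, part of the marker is inside the outcome. If treatment is missing from both models, a drug that shifts marker and outcome by unconnected routes makes them correlate across the pooled subjects. In either case a significant term could be reported as the mechanism explaining the clinical effect. The synopsis says these endpoints are meant to inform understanding of mechanism and potential efficacy, so that misreading is what is at stake.

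**Working it through.** **The plan's own figure.** The protocol gives no figure for the model comparison. Its only precision figure for this outcome is in Section 9.2.1: 95% half-widths of 0.693 and 0.490 for change in DAS28-CRP, with SD 1 and n = 8 and 16. These reproduce as 1.96 × 1/√8 = 0.693 and 1.96 × 1/√16 = 0.490.

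**Inputs.** From the protocol: 16 active and 8 placebo subjects on TID (Section 9.2.1), 2:1 allocation (Section 6.2), and at most 18 BID subjects, so a pooled N of up to 24 + 18 = 42 (28 and 14). Assumed, because the protocol does not give them: two-sided 5% level, CRP's share of the variance of DAS28-CRP change, and the size of the drug effects. Method: a 1-df F-test of adding the marker to the null model, in 6,000 simulated trials per setting. With no correlation the test rejects in 4.8% (N = 24) and 5.1% (N = 42).

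**1. Overlap alone.** Let C be CRP's contribution and R all other components, standardised and independent, with the drug inert on both. With w the CRP share, outcome change is √w·C + √(1−w)·R, so the correlation between C and the outcome is √w.

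| CRP share w | Correlation √w | N = 24, treatment not in models | N = 24, treatment in both | N = 42, treatment not in models |
|---|---|---|---|---|
| 5% | 0.22 | 18.6% | 17.7% | 29.7% |
| 10% | 0.32 | 32.8% | 31.5% | 54.4% |
| 20% | 0.45 | 60.9% | 58.7% | 86.6% |
| 30% | 0.55 | 81.9% | 79.9% | 97.2% |
| 40% | 0.63 | 93.7% | 92.4% | 99.4% |

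Hand check by the Fisher transformation, rejection ≈ Φ(atanh(√w)·√(N−3) − 1.96), with √21 = 4.583:
- w = 5%: 0.2275 × 4.583 − 1.96 = −0.92, giving 18%
- w = 10%: 0.3275 × 4.583 − 1.96 = −0.46, giving 32%
- w = 20%: 0.4812 × 4.583 − 1.96 = 0.25, giving 60%

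The treatment columns differ little, so adjusting for arm does not remove the coupling. These figures are for CRP itself as the marker. For the Vectra DA score the overlap correlation would be √(v·w), with v CRP's share of that score. This is smaller by an amount the protocol does not let one compute. Other individual markers, such as IL6, have no such overlap.

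**2. Separate drug effects.** Suppose the drug shifts marker and outcome each by d SD, with no correlation within arm. With p = 16/24 = 2/3, p(1−p) = 2/9 and the pooled correlation is (2/9)d² / (1 + (2/9)d²). For d = 1 this is 0.222/1.222 = 0.18. For d = 1.5 it is 0.5/1.5 = 0.33. Rejection at N = 24:

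| Effect d | Treatment not in models | Treatment in both |
|---|---|---|
| 1 SD | 13.9% | 5.4% |
| 1.5 SD | 38.1% | 4.8% |
| 2 SD | 71.7% | 4.9% |

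**3. Target engagement.** Take engagement near 0 on placebo and near 0.97 on active, unrelated to DAS28 within arm. With treatment omitted the marker simply stands in for arm: 20% and 60% rejection at drug effects of 0.5 and 1 SD, matching the treatment test itself. With treatment included it is about 5%.

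**The case against.** Several points on the other side stand.

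- The comparison is an option, multivariate methods are also allowed, and covariates are ordinary RAP content. A reader might infer that treatment is left out of the models. The null is defined only by the absence of mechanistic terms, so part 2 is conditional on something the text leaves open. For the same reason it cannot be said that the test picks up only subject-level correlation.
- A reader might infer that the protocol names CRP as a mechanistic predictor of DAS28-CRP. It does not. Section 9.3.2 lists inflammatory biomarkers beside mechanistic endpoints and gives only target engagement as an example of the latter: "Additional inflammatory biomarkers, clinical and mechanistic endpoints (e.g. target engagement) may be reviewed if available". The pairing is within plan through Section 9.1 and the endpoint list, but it is not prescribed.
- Section 4.4 notes that "autoimmune diseases naturally fluctuate in severity", which could move marker and outcome together in both arms. At an assumed correlation of 0.3 or 0.5 and an inert drug, the test rejects in 30% or 73% of trials. A reader might call these false positives. They are not: the association is real and the test detects it correctly. Only the word explains would be wrong, and under a plain reading of predicts the test is apt, apart from the CRP overlap.
- For ACR response, CRP is one of five measures of which three must improve (Section 7.4.2.2), so the coupling is looser. No figure was computed.

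One tempting remedy should also be resisted: requiring an association stronger than that on placebo. A true mediator can have the same slope in both arms, and such a rule would then reject a genuine mechanism. Nor can 8 placebo subjects support the contrast: an observed correlation of 0.3 has 95% limits tanh(0.3095 ± 1.96/√5), about −0.51 to 0.83.

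None of this lets an association test support a claim about explaining the drug's effect, and none of it removes the overlap when a CRP-containing marker is set against a CRP-containing score.

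**Conclusion.** The point holds in this form: the inference stated in Section 9.4.2 is stronger than the comparison it describes, and two permitted set-ups can produce significance without a mechanistic link. CRP overlap gives about 19 to 61% rejection at assumed CRP shares of 5 to 20%, with or without treatment in the models. Omitting treatment gives 14% or 38% for separate effects of 1 or 1.5 SD. All rest on N = 24, a nominal 5% level and assumed shares or effects. They show how the test would behave under those assumptions and are not the plan's error rate.

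A reader might infer that a futility decision hangs on this model. Section 9.3.2 mentions an interim look at clinical and mechanistic data but does not tie it to this comparison. The analysis is secondary, not formally tested and in a study not powered for differences, so the priority is modest.

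**What to change.** Amend Section 9.4.2, and carry the change into the RAP, so that:

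- (a) when the marker is CRP or a score containing CRP, the clinical outcome is the CRP-free components of DAS28: tender joint count, swollen joint count and PtGA. With no true correlation, rejection returns to about 5% (4.8% at N = 24, 5.1% at N = 42).
- (b) treatment arm and baseline values are in both the null and the extended model. This takes the parallel-shift rejection from 14% and 38% to about 5%.
- (c) results are described as association or prediction, not as explaining the drug's effect.

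All the components are already collected, so the cost is wording, one or two degrees of freedom, and associations that will look weaker. The real loss is for target engagement. It nearly coincides with treatment arm (Section 4.5 predicts that about 90% of TID subjects exceed 96% engagement at trough), so with treatment in the model little is left to estimate within arm. The report should say so.

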### **9.4.3. Other Analyses**

In addition, based on the data that we observe in the study, probabilities of success will be determined, where the definition of success will be dependent on the endpoint. For example, what is the probability that we would observe a certain change in DAS28 (i.e., comparator rate), based on the data that we have observed in the study.

GSK2982772 plasma concentrations will be summarised descriptively by day and nominal sampling time.

Further details regarding the statistical analysis will be outlined in the Reporting and Analysis Plan (RAP).

#### **9.4.3.1. Exploratory Analyses**

All exploratory endpoints will be descriptively summarised, graphically presented and listed appropriately. Further details can be found in the RAP.

## **10. STUDY GOVERNANCE CONSIDERATIONS**

### **10.1. Posting of Information on Publicly Available Clinical Trial Registers**

Study information from this protocol will be posted on publicly available clinical trial registers before enrollment of subjects begins.

### **10.2. Regulatory and Ethical Considerations, Including the Informed Consent Process**

The study will be conducted in accordance with all applicable regulatory requirements, and with GSK policy.

The study will also be conducted in accordance with ICH Good Clinical Practice (GCP), all applicable subject privacy requirements, and the guiding principles of the current version of the Declaration of Helsinki. This includes, but is not limited to, the following:

- IRB/IEC review and favorable opinion/approval of the study protocol and amendments as applicable.
- Obtaining signed informed consent.
- Investigator reporting requirements (e.g., reporting of AEs/SAEs/protocol deviations to IRB/IEC).

- GSK will provide full details of the above procedures, either verbally, in writing, or both.
- Signed informed consent must be obtained for each subject prior to participation in the study.
- The IEC/IRB, and where applicable the regulatory authority, approve the clinical protocol and all optional assessments, including genetic research.
- Optional assessments (including those in a separate protocol and/or under separate informed consent) and the clinical protocol should be concurrently submitted for approval unless regulation requires separate submission.
- Approval of the optional assessments may occur after approval is granted for the clinical protocol where required by regulatory authorities. In this situation, written approval of the clinical protocol should state that approval of optional assessments is being deferred and the study, with the exception of the optional assessments, can be initiated.

### **10.3. Quality Control (Study Monitoring)**

- In accordance with applicable regulations including GCP, and GSK procedures, GSK monitors will contact the site prior to the start of the study to review with the site staff the protocol, study requirements, and their responsibilities to satisfy regulatory, ethical, and GSK requirements.
- When reviewing data collection procedures, the discussion will also include identification, agreement and documentation of data items for which the CRF will serve as the source document.

GSK will monitor the study and site activity to verify that the:

- Data are authentic, accurate, and complete.
- Safety and rights of subjects are being protected.
- Study is conducted in accordance with the currently approved protocol and any other study agreements, GCP, and all applicable regulatory requirements.

The Investigator and the head of the medical institution (where applicable) agrees to allow the monitor direct access to all relevant documents.

### **10.4. Quality Assurance**

- To ensure compliance with GCP and all applicable regulatory requirements, GSK may conduct a quality assurance assessment and/or audit of the site records, and the regulatory agencies may conduct a regulatory inspection at any time during or after completion of the study.
- In the event of an assessment, audit or inspection, the Investigator (and institution) must agree to grant the advisor(s), auditor(s) and inspector(s) direct access to all relevant documents and to allocate their time and the time of their staff to discuss the conduct of the study, any findings/relevant issues and to implement any corrective and/or preventative actions to address any findings/issues identified.

## 10.5. Study and Site Closure

- Upon completion or premature discontinuation of the study, the GSK monitor will conduct site closure activities with the Investigator or site staff, as appropriate, in accordance with applicable regulations including GCP, and GSK Standard Operating Procedures (SOP).
- GSK reserves the right to temporarily suspend or prematurely discontinue this study at any time for reasons including, but not limited to, safety or ethical issues or severe non-compliance. For multicenter studies, this can occur at one or more or at all sites.
- If GSK determines such action is needed, GSK will discuss the reasons for taking such action with the Investigator or the head of the medical institution (where applicable). When feasible, GSK will provide advance notification to the Investigator or the head of the medical institution, where applicable, of the impending action.
- If the study is suspended or prematurely discontinued for safety reasons, GSK will promptly inform all Investigators, heads of the medical institutions (where applicable) and/or institution(s) conducting the study. GSK will also promptly inform the relevant regulatory authorities of the suspension or premature discontinuation of the study and the reason(s) for the action.
- If required by applicable regulations, the Investigator or the head of the medical institution (where applicable) must inform the IRB/IEC promptly and provide the reason for the suspension or premature discontinuation.

## 10.6. Records Retention

- Following closure of the study, the Investigator or the head of the medical institution (where applicable) must maintain all site study records (except for those required by local regulations to be maintained elsewhere), in a safe and secure location.
- The records must be maintained to allow easy and timely retrieval, when needed (e.g., for a GSK audit or regulatory inspection) and must be available for review in conjunction with assessment of the facility, supporting systems, and relevant site staff.
- Where permitted by local laws/regulations or institutional policy, some or all of these records can be maintained in a format other than hard copy (e.g., microfiche, scanned, electronic); however, caution needs to be exercised before such action is taken.
- The Investigator must ensure that all reproductions are legible and are a true and accurate copy of the original and meet accessibility and retrieval standards, including re-generating a hard copy, if required. Furthermore, the Investigator must ensure there is an acceptable back-up of these reproductions and that an acceptable quality control process exists for making these reproductions.

- GSK will inform the Investigator of the time period for retaining these records to comply with all applicable regulatory requirements. The minimum retention time will meet the strictest standard applicable to that site for the study, as dictated by any institutional requirements or local laws or regulations, GSK standards/procedures, and/or institutional requirements.
- The Investigator must notify GSK of any changes in the archival arrangements, including, but not limited to, archival at an off-site facility or transfer of ownership of the records in the event the Investigator is no longer associated with the site.

